This is due to the fact that “soft silicone dressing have been shown to prevent trauma to the wound bed and periwound skin and have been described as ‘atraumatic’”.¹⁴ Other benefits of soft silicone dressings include the ability to conform to anatomical contours, a reduction in scar development, and reduced overall cost secondary to improved wound healing and need for less frequent dressing changes.¹⁴

Mepitel Ag, a hybrid type soft silicone dressing impregnated with a silver compound was recently approved for use in partial thickness burns and partial and full thickness grafts.¹⁵ This combination of soft silicone and silver provides a relatively pain free dressing with broad spectrum antibiotic coverage. The aim of this study is to demonstrate that Mepitel Ag in combination with a soft cast technique is a superior alternative to antibiotic ointment impregnated gauze and soft cast for the treatment of pediatric hand and foot burns due to decreased healing time, decreased patient pain and lower yeast infection rates.

IV. Research Methods

A. Outcome Measure(s):

Primary outcomes utilized in this study include overall wound outcome, measured in length of days to re-epithelialization or need for surgical intervention, clinical assessment and wound progression photographs. Secondary outcomes include number of patients requiring surgical debridement, presence of infection based on odor, rash, deep red appearance or puritis. These wounds will not be cultured, patient pain level with dressing change based on the FLACC (Face, Legs, Activity, Cry, Consolability) scale, parents perceived level of pain, pain level at home based on family reported pain and pain medication use. We will also assess cost effectiveness of dressings including the number of clinic visits, number of soft casts, and the cost and amount of dressings used over the course of treatment.

B. Description of Population to be Enrolled:

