Patients to be included in this study will be all Children's Hospital Colorado burn patients between the ages of 31 days and 18 years with newly diagnosed partial to deep partial or full thickness hand or foot burns, including bilateral or unilateral injury. Each injured extremity will serve as a separate data point. Exclusions include age > 18 years at start of study, silver allergy, silicone allergy, electrical or chemical burn, past medical history of immunodeficiency disorders such as diabetes mellitus, AIDs, or HIV, pregnant women, prisoners children under the protection of the department of human services, and the decisionally challenged.

C. Study Design and Research Methods

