New burn clinic patients identified with a partial to deep partial or full thickness hand or foot burn will be randomized into either the Mepitel Ag group or the control group on their first clinic visit based on burn wound severity and age using RedCap. The randomization scheme in RedCap will be independently created by a statistician. Parental consent and or patient assent will be obtained prior to initial dressing. Burn severity will be clinically determined by one provider and one burn nurse during initial exam based on a 10 point burn severity classification scale in regards to the following parameters: 1) Superficial first degree- wound appears pink or red, involves epidermis only, no blisters present, dry; 2) Second degree, superficial partial thickness- burn involves epidermis + dermis, red or bright pink in color with blisters and or swelling, blanches, moist appearing; 3) Second degree, majority superficial partial thickness, minority superficial- burn involves majority ($\geq 66\%$) superficial partial thickness, epidermis + dermis, red or bright pink in color with blisters and or swelling, blanches, moist appearing, minority ($\sim 33\%$ or less) superficial first degree with areas of redness but no blistering; 4) Second degree, majority partial thickness, minority deep partial thickness- majority of burn ($\geq 66\%$) epidermis + dermis, red or bright pink in color, moist, less than half of burn ($\sim 33\%$ or less) is deep with pale pink-white areas, may or may not have a marbled or mosaic appearance; 5) Second degree, deep partial thickness- involves epidermis + dermis, pale pink to white in color, may have thin white moist eschar, may or may not have a marbled or mosaic type appearance, moist; 6) Second degree, majority deep partial thickness, minority superficial partial thickness- minority of burn ($\sim 33\%$ or less) involves epidermis + dermis, red or bright pink in color, moist, majority ($\geq 66\%$) of burn is deep with pale pink-white areas having a marbled or mosaic appearance, may or may not have thin white moist eschar, skin buds may or may not be present; 7) Second degree, deep partial thickness with areas of full thickness- majority of burn ($\geq 66\%$) involves epidermis + dermis, pale pink to white in color, may have thin white moist eschar, may or may not have a marbled or mosaic type appearance, moist, skin buds may or may not be present, minority of burn ($\sim 33\%$ or less) demonstrates thin to thick area of eschar white, brown or black in color, may need skin graft to heal; 8) Third degree full thickness with minority partial thickness- majority of burn ($\geq 66\%$) involves entire dermis + epidermis, thin to thick eschar that is white, brown or black in color, dry appearing, minority of burn ($\sim 33\%$ or less) is pink or red and moist, with blisters and or swelling, blanches; 9) Third degree full thickness- involves entire dermis + epidermis, thin to thick eschar that is white,

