
brown or black in color, dry appearing; 10) Fourth degree- third degree + muscle and or bone involvement. The provider and burn nurse will each give the patient a number and the severity will be determined based on the average of the 2 numbers. Any patient given a number 2, 3 or 4, will be placed into the "partial thickness" category, any patient given a 5, 6, or 7 will be placed into the "deep partial thickness" category, and lastly, any patient given an 8 or 9 will be placed into the "full thickness" category for burn severity.

Patients will be randomized into one of two groups, Mepitel Ag or standard TAO, using RedCap and based on a random clinical trial excel spread sheet balanced by burn severity. A statistician will provide a randomization scheme for investigators to follow. Photographs will be taken prior to dressing application at the initial visit and each subsequent visit. ~~Patient wounds will be dressed in either Mepitel Ag, kling or kerlex, cast padding, gypsoma plaster, soft cast material and coban for up to 21 days or until complete re-epithelialization of the wound occurs or unless surgery is indicated; the control, standard dressing of Triple Antibiotic Ointment impregnated adaptic gauze, kling or kerlex, cast padding, gypsoma plaster, soft cast material and coban for 10-14 days, or Nystatin impregnated adaptic, kling or kerlex, cast padding, gypsoma plaster, soft cast material and coban for 8-21 days or until complete re-epithelialization of the wound occurs or surgery is indicated. The SCT is applied by Occupational and Physical trained in casting and positioning. The soft cast provides optimal positioning while eliminating friction on the burn area. Dressing changes will occur every 3-10 days and will be determined by the provider, based on burn wound severity. Upon each return clinic visit, the patient will have their wound severity assessed by the following scoring system: 1=0% healed, 2=20% healed; 3=40% healed; 4=60% healed; 5=80% healed; 6=100% healed. This will be established by provider and burn nurse examination of the wound. This will be recorded in RedCap:_____~~

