A member of the nursing team will also complete a questionnaire at each follow up visit to indicate pain level with dressing change based on the FLACC scale, parents perceived level of pain during dressing change, parental reported pain level at home, use of home pain medications, type of home pain medication- narcotic vs non-narcotic, clinical assessment of yeast rash including odor, visible rash, use of fluconazole, ease of dressing application, and amount and type of product used in dressing change.

D. Description, Risks and Justification of Procedures and Data Collection Tools:

A photography release will be distributed and signed by parent at initial visit.

Anursing questionnaire will be completed by nursing staff at each follow up appointment.

Local wound care including cleansing, wound measurement and dressing change will be performed by burn team including nursing staff and occupational and physical therapists. Although punch biopsy with histological analysis is considered the 'gold standard' in assessing burn wound depth, it is invasive and time consuming.¹⁸ Clinical assessment remains the most frequent and rapid method.¹⁸ Due to the time sensitive nature of the proposed trial and in order to avoid delaying wound care and initial dressing application, a 10 point clinical assessment scale has been created, as listed above for use in determining initial burn wound severity. Patient wound depth will be clinically determined by the average of the scores from the provider and the burn nurse.

The wound will also be assessed by the provider and nurse on subsequent visits using the following scoring tool: 1=0% healed, 2=20% healed; 3=40% healed; 4=60% healed; 5=80% healed; 6=100% healed. This will be established by provider and burn nurse examination of the wound. This will be recorded in RedCap.

The overall risk for this study is minimal, with no foreseen adverse reactions. The risk of a silver allergy or adverse reaction to silicone is very rare.

E. Potential Scientific Problems:

Limitations to the proposed study design include varying diagnostic opinions between provider and burn nurse for the determination of superficial vs deep partial thickness burn wounds based on clinical assessment, provider or nurse bias based on dressing preference, and possible uneven trial groups.

F. Data Analysis Plan:

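### Burns at other sites are neither excluded nor named as a data item, so home pain, pain medication and clinic visits can partly reflect burns outside the randomised comparison

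*Combined protocol and SAP*

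**What the plan says.** Eligibility is set in section IV.B. The qualifying injury is described as "newly diagnosed partial to deep partial or full thickness hand or foot burns, including bilateral or unilateral injury". The population is otherwise open to every burn patient of the hospital in the age range, and the exclusions begin "Exclusions include age > 18 years at start of study, silver allergy, silicone allergy, electrical or chemical burn" and go on to immunodeficiency, pregnancy and vulnerable groups. Burns at other sites are not mentioned, and there is no limit on body surface burned. The same section adds: "Each injured extremity will serve as a separate data point".

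Section IV.C describes allocation twice, once as "on their first clinic visit based on burn wound severity and age using RedCap" and once as "based on a random clinical trial excel spread sheet balanced by burn severity". The 10-point scale behind burn severity grades depth, not the extent or site of other burns.

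The nursing questionnaire in IV.C records "pain level with dressing change based on the FLACC scale, parents perceived level of pain during dressing change, parental reported pain level at home", home pain medication and whether it is a narcotic, signs of yeast, fluconazole use, and the dressing products used. On cost, IV.A says: "We will also assess cost effectiveness of dressings including the number of clinic visits".

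Section IV.F compares pain levels and pain medication by t-tests and chi-squared tests with no covariates. It uses logistic regression for yeast infection and surgical debridement, and says only that cost effectiveness will be analysed. It also promises a comparison of baseline clinical characteristics between arms, without listing them.

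**The concern.** A child with a hand burn and a second burn elsewhere meets the entry criteria as written. What the family reports about pain at home, what analgesic is given and how often the child returns to clinic belong to the child, not to the hand. Part of each can come from the second burn, which the comparison of Mepitel Ag with triple antibiotic ointment does not address.

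Less pain is one of the three benefits named in the hypothesis, and clinic visits are a component of the cost outcome. If other burns are common and painful, they add variance to these comparisons and lower power. In the affected children they may also mask part of any dressing effect. Unless the fact is recorded, the analysis cannot take account of it.

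**Working it through.** **The plan's own power figure.** Section IV.F claims over 90% power for a 2-day difference with SD 0.3, alpha 0.05 and 50 per group. Recalculation gives about 100%, so the stated bound holds. That figure concerns days to healing. The plan has no power calculation for pain, so what follows is an illustration.

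**Inputs.** From the plan: 50 per group and alpha 0.05 (taken as two-sided). Assumed, because the documents give no figures: pain SD 2 points in children with isolated hand or foot burns; a dressing effect detectable with 80% power in those children; a share q with other burns; a pain rise of k points in them. The 100 data points are treated as 100 independent children.

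**Step 1: detectable effect.** Two-sample t-test (noncentral t), n = 50 per arm, SD 2: 80% power at a difference of 1.13 points.

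**Step 2: added variance.** Total variance = 4 + q(1 − q)k². For q = 0.2 and k = 2 this is 4 + 0.16 × 4 = 4.64, so the SD is 2.15. Power to detect 1.13 points is then:

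| Share q | Rise k | Variance | SD | Power |
|---|---|---|---|---|
| 5% | 1 | 4.05 | 2.01 | 79.5% |
| 10% | 1 | 4.09 | 2.02 | 79.1% |
| 5% | 2 | 4.19 | 2.05 | 78.2% |
| 10% | 2 | 4.36 | 2.09 | 76.5% |
| 20% | 2 | 4.64 | 2.15 | 73.9% |
| 30% | 2 | 4.84 | 2.20 | 72.1% |
| 20% | 3 | 5.44 | 2.33 | 67.1% |
| 30% | 3 | 5.89 | 2.43 | 63.6% |

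At k = 2 and q = 20-30%, the variance ratio is 4.64/4 = 1.16 to 4.84/4 = 1.21, equivalent to needing 16-21% more children.

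**Step 3: dilution, as an extreme case.** Suppose the dressing effect is zero in every child with another burn, so the mean effect is 1.13 × (1 − q). At k = 2, power is 55% for q = 20% and 43% for q = 30%. Adjusting for other burns brings the SD back to 2 but leaves the smaller mean effect; power rises only to 61% and 50%.

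**Step 4: chance imbalance.** The SD of the between-arm difference in share is √(2q(1 − q)/50): 8.0 percentage points at q = 20% and 9.2 at q = 30%. A gap of 10 points or more occurs in about 26% and 33% of trials respectively (exact binomial). With k = 2, a 10-point gap shifts the pain difference by 0.10 × 2 = 0.2 points, against a standard error of 2 × √(2/50) = 0.4. This variation is already in the inflated SD of Step 2 and is not a further loss.

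**The case against.** The strongest case against is that this is an optional precision covariate for secondary outcomes. Randomisation balances other burns on average, the primary outcome is measured on the wound, and the documents do not show that such children are common. At a 5-10% share the loss from added variance is at most about 3.5 percentage points of power. All of this stands, and it limits the priority of the point.

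A reader might infer more than the documents support:

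- **That other burns will go unrecorded and an imbalance could never be seen.** The baseline clinical characteristics in IV.F are undefined, IV.D mentions wound measurement, and the RedCap first-visit form is not among the documents. What can be said is that no named item records other burns and nothing commits the trial to collecting them.
- **That every child-level outcome gets an unadjusted t-test or chi-squared test.** IV.F says this only of pain levels and pain medication. Yeast infection is analysed by logistic regression, and no method is named for clinic visits.
- **That all pain measures are equally exposed.** FLACC and one parent rating are tied to the dressing change, so they are less affected. They are reached mainly if another burn is dressed at the same visit, and the documents do not say how or where other burns are dressed.
- **That a material imbalance is likely.** Under the 20-30% assumption, a 10-point gap arises in about a quarter to a third of trials.
- **That power for pain falls to 43-55%.** This requires the dressing effect to vanish in every child with another burn, for which there is no evidence.

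Counting extremities as data points is a separate matter. If some children contribute two extremities, there are fewer than 100 independent children and the power figures here are optimistic.

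**Conclusion.** The point holds as a modest weakness in secondary outcomes. Entry of children with other burns follows from the open inclusion wording and the absence of an exclusion; the plan does not state it outright. It bears most on home pain, home pain medication and clinic visits, less on pain at the dressing change, and not on time to re-epithelialisation. It causes no systematic bias.

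The size depends on two unknowns, the share of children affected and the pain their other burns add. Across the ranges shown, power from added variance alone falls from 80% to between about 64% and just under 80%. The lower end needs both a 30% share and a 3-point rise. These figures are for a continuous pain score only; they rest on an assumed SD of 2 and 50 independent children per arm, and were not computed for medication use or visits.

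The change is worth making because it is cheap and is more credible fixed in advance than chosen after open-label results are seen.

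**What to change.** 1. Add a field to the first-visit RedCap form, completed before allocation: other burns needing dressing (yes/no). Add total percent body surface burned as a baseline descriptor, reported by arm and not used as a covariate.
2. In IV.F, replace the unadjusted pain and pain-medication tests with regression on treatment, adjusted for other burns (yes/no): linear for pain scores and logistic for medication use. State that the odds ratio is conditional on that covariate. Name a method for clinic visits and use the same covariate.
3. Prespecify a sensitivity analysis that repeats these comparisons in children whose only burns are on the hands or feet. State that it has fewer children (at a 20-30% share, 50 × 0.8 = 40 to 50 × 0.7 = 35 per arm), and that the adjusted analysis in all children restores precision but does not undo dilution.

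The cost is two baseline fields, one degree of freedom per model and one extra table. Eligibility, allocation, sample size and care do not change.

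### Both limbs of a bilaterally burned child count as separate observations, but the healing-time analysis names no method for within-child correlation

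*Combined protocol and SAP*

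**What the plan says.** Section IV.B makes children eligible with hand or foot burns "including bilateral or unilateral injury", and sets a general rule: "Each injured extremity will serve as a separate data point".

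Section IV.C works at the level of the child. Children are randomised "on their first clinic visit based on burn wound severity and age using RedCap". Severity is also scored per child: "The provider and burn nurse will each give the patient a number", and the two numbers are averaged. Allocation is described again in the same terms: "Patients will be randomized into one of two groups, Mepitel Ag or standard TAO", "based on a random clinical trial excel spread sheet balanced by burn severity". Nothing says whether the two limbs of one child receive one allocation or two, or one severity category or two.

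Section IV.F plans Kaplan-Meier curves, a log-rank test and a Cox model for days to re-epithelialisation, logistic regression for debridement and yeast infection, and t-tests and chi-squared tests for pain and pain medication. It names no robust variance, frailty term, GEE, mixed model or one-limb-per-child rule. Censoring at surgery is worded for patients.

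Section IV.A defines one secondary outcome as the "number of patients requiring surgical debridement" and another as "patient pain level with dressing change based on the FLACC" scale. Section IV.F.1 gives the group size as 50 subjects and the total as 100 burns.

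**The concern.** In their ordinary form, the log-rank test, the Cox model and logistic regression assume independent observations. Two burns on one child share age, cause of injury, care and healing capacity, so their healing times are likely to be correlated. Counting them as independent misstates the variance of the treatment comparison.

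The direction depends on a rule the plan omits. With both limbs in the same arm, the second limb brings less new information than the analysis credits, and the variance is understated. With limbs in opposite arms, the shared child effect cancels from the comparison, and the variance is overstated.

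The per-extremity rule also sits beside patient wording for censoring, debridement and group size. An analyst cannot tell whether surgery on one limb ends follow-up of the other, or how many children stand behind 100 burns. If these choices are left until the data are in, they become post-hoc choices about the main result.

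**Working it through.** **1. The plan's own figure.** Inputs from section IV.F.1: difference 2 days, SD 0.3, alpha 0.05 (two-sided assumed), 50 per group. SE = 0.3 × √(2/50) = 0.06, and 2/0.06 = 33.3 standard errors, so power is about 100%. The stated figure of over 90% is met as a lower bound. The calculation contains no design effect.

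**2. Inputs the documents do not give.** Let q be the share of burns that belong to bilateral pairs and ρ the within-child correlation. I assume q = 0.2-0.5 and ρ = 0.3-0.8.

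**3. Formula, ignoring severity balancing.** Each paired burn covaries with one partner, so the variance is multiplied by DE = 1 + qρ (shared arm) or 1 − qρ (opposite arms). For 100 burns, children = 100 × (1 − q/2). With a shared arm, effective n = 100/DE. True alpha = 2 × [1 − Φ(1.96/√DE)].

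| q | ρ | Children | DE, shared arm | Effective n | Alpha, shared | DE, opposite arms | Alpha, opposite |
|---|---|---|---|---|---|---|---|
| 0.2 | 0.3 | 90 | 1.06 | 94 | 5.7% | 0.94 | 4.3% |
| 0.2 | 0.8 | 90 | 1.16 | 86 | 6.9% | 0.84 | 3.2% |
| 0.5 | 0.3 | 75 | 1.15 | 87 | 6.8% | 0.85 | 3.4% |
| 0.5 | 0.8 | 75 | 1.40 | 71 | 9.8% | 0.60 | 1.1% |

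A mild shared-arm case, q = 0.1 and ρ = 0.3, gives DE = 1.03, alpha 5.3% and effective n 97.

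**4. Simulation of the planned test.** Section IV.C balances allocation by severity. That removes some between-severity variation from the treatment difference but leaves it in the variance of an unadjusted test, which makes the test conservative. The simulation therefore built the balancing in, with no treatment effect. Further assumptions: permuted blocks of 4 within three severity strata (45/45/10%); severity explaining 10%-30% of the variance of log healing time; lognormal or Weibull times; and either no censoring or surgery in about 15% of burns. There were 6,000 runs per shared-arm cell and 4,000 per opposite-arm cell. Ranges marked "about" also allow for separate uncensored runs with their own assumed severity effects.

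| Test and allocation | No pairs | q = 0.2 | q = 0.5 |
|---|---|---|---|
| Unadjusted log-rank, shared arm | about 2%-5% | about 2%-6.5% | about 3%-9% |
| Severity-stratified log-rank, shared arm | 4.9%-5.7% | about 6%-11% (both q) | as left |
| Unadjusted log-rank, opposite arms | – | 0.4%-4.1% (both q) | as left |

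In the main runs, the unadjusted shared-arm test exceeded 5% in 4 of 24 cells at q = 0.2 and 15 of 24 at q = 0.5. The top of each shared-arm range at q = 0.5 needs ρ = 0.8.

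**5. Does clustering repair it?** A severity-stratified Cox model with variance clustered on child, multiplied by K/(K − 4) for K children and with a t reference, rejected 4.9%-6.0% (shared arm) and 3.5%-6.0% (opposite arms). A clustered score test without a small-sample correction rejected 6%-8% with a shared arm, so the correction matters.

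**6. Effect on stated power.** At DE = 1.40 there are 50/1.40 = 35.7 effective burns per group. SE = 0.3 × √(2/35.7) = 0.071, and 2/0.071 = 28 standard errors. Power stays at about 100%.

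**The case against.** The strongest reply is that the planned test may do little harm. Section IV.F names no covariates for the log-rank or Cox analysis, and severity-balanced allocation makes the unadjusted test conservative. With 20% of burns in pairs it is mostly at or below 5%. This stands, and it limits the size of the point. It does not remove the defect: two errors partly cancel by an amount nobody has planned, and a severity-stratified analysis loses the offset.

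It is also true that q, ρ, the block size, the strata shares, the severity effect and the surgery rates are all assumptions. The gap in the text is certain; its size is not.

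A reader might infer three stronger things that the documents do not support:

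- **That the primary test rejects about 10% of the time under the null.** The formula's 9.8% ignores severity balancing, and the 6%-11% range belongs to a stratified test that the plan does not propose.
- **That the trial is underpowered.** At the stated SD of 0.3, clustering leaves power at about 100%.
- **That the plan has no unit of analysis.** Section IV.B sets one, the extremity, and the total of 100 burns agrees with it. The fair criticism is that the patient wording for censoring, debridement and group size conflicts with that rule.

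**Conclusion.** The point holds as a specification gap that should be fixed. Limbs are analysed as independent although children are randomised, and nothing elsewhere in the plan repairs this. The standard error for healing time is wrong whenever bilateral children with correlated burns are enrolled. It is too small if limbs share an arm, which the patient wording implies but does not state, and too large if they are split.

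For the log-rank test as planned, the likely consequence is modest: at most about 6.5% at q = 0.2 and about 9% at q = 0.5, the latter only with a correlation near 0.8. If few children are bilateral it is close to nil. Confidence is high in the textual gap and much lower in these figures, which depend on the assumed inputs.

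**What to change.** 1. **IV.C:** state whether both limbs of a bilateral child receive one allocation and one severity category.
2. **IV.F, healing time:** use a within-child method. One choice is a Cox model with robust variance clustered on child and a small-sample correction, stratified by the severity categories actually used in randomisation. Take the hazard ratio, confidence interval and p-value from that one model. A shared-frailty Cox model or a clustered log-rank test is an acceptable alternative. The categories must first cover every score: an average of 4.5 or 7.5, or a score of 1 or 10, has no category in IV.C.
3. **IV.A and IV.F, units:** reconcile the unit for each outcome with the per-extremity rule, including whether censoring at surgery applies to the operated limb or to the child. Use child-clustered GEE or mixed models for outcomes recorded per limb. Analyse outcomes recorded once per child, such as home pain and pain medication, once per child. State which unit applies to debridement.
4. **IV.F.1:** report children and burns separately, with an effective sample size under an assumed design effect.

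The cost is protocol wording and standard software options. If limbs share an arm, intervals become slightly wider and the stated effective sample size smaller. No extra patients or data are needed.

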Analysis Plan: Demographic and clinical characteristics will be summarized and compared between the two treatment groups using chi-squared and two-sample t-tests for categorical and continuous data, respectively. For analysis of the primary outcome, time to wound healing, we will use Kaplan-Meier curves, the log-rank test and a Cox proportional hazards model to determine the difference in days to re-epithelialization between the TAO and Mepitel Ag soft cast methods. Patients that require surgical intervention will be censored at the time of surgery. Logistic regression will be used to analyze the secondary outcomes, need for surgical debridement and occurrence of yeast infection. Pain level outcomes and pain medication use will be compared using two-sample t-tests and chi-squared tests. Cost effectiveness outcomes will also be analyzed.

1. Sample size: A statistical power analysis was performed to estimate power, based on results reported in A Soft casting Technique to Manage Pediatric Hand Burns: Less Pain, Greater Gain.²² Considering the simplest between group comparison and assuming a standard deviation of 0.3, alpha of 0.05 and 50 subjects per group there is over 90% power to detect a difference of 2 days between the treatment groups. Thus, we expect that our proposed sample size of 100 burns will be adequate for the main objective of this study.

G. Summarize Knowledge to be Gained:

To demonstrate that Mepitel Ag in combination with a soft cast technique improves wound healing in pediatric partial to deep partial thickness hand and foot burns by decreasing the length of healing time, decreasing the risk of yeast infection, and decreasing pain associated with dressing changes.

H. References:

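### Counting every injured extremity as a data point enters child-level outcomes twice for children with two burned limbs, so the planned t-tests and chi-squared tests on them are too liberal

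*Combined protocol and SAP*

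**What the plan says.** **Unit of analysis.** Section IV.B admits burns of hand or foot, "including bilateral or unilateral injury", and then states "Each injured extremity will serve as a separate data point". It exempts no outcome.

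**Unit of randomization.** Section IV.C states "Patients will be randomized into one of two groups, Mepitel Ag or standard TAO". Burn severity is also scored once per patient there.

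**Outcomes.** Section IV.A lists "patient pain level with dressing change based on the FLACC" scale, then "parents perceived level of pain, pain level at home based on family reported pain and pain medication use". It adds: "We will also assess cost effectiveness of dressings including the number of clinic visits, number of soft casts", together with the cost and amount of dressings. Section IV.C has nursing staff complete a questionnaire at each follow-up visit. It does not say whether the form is filled in per child or per limb.

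**Analysis.** Section IV.F states "Pain level outcomes and pain medication use will be compared using two-sample t-tests and chi-squared tests". Demographic and clinical characteristics are compared with the same two tests. For cost, IV.F says only that the outcomes will be analysed. Healing time is analysed by Kaplan-Meier, log-rank and Cox methods, with the rule "Patients that require surgical intervention will be censored at the time of surgery". Surgical debridement and yeast infection are analysed by logistic regression. The section contains no one-record-per-child rule, clustering term, GEE, mixed model or robust variance. Its sample size paragraph counts 50 subjects per group in one sentence and 100 burns in the next.

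**The concern.** A child has one age, one home pain report, one answer on home medication and one count of clinic visits. Applied as written, the extremity rule gives a child with two burned limbs two rows carrying the same value for each of these. Because the patient is randomized, both rows fall in the same arm. The two-sample t-test and the chi-squared test treat them as two independent observations, so standard errors are too small and p-values too low. Children with two burned limbs also get double weight in the estimate.

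Less pain at dressing changes is one of the three stated hypotheses (section I), and pain is part of specific aim 2. A falsely significant pain result would therefore support a superiority claim.

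A milder form of the problem affects the limb-level outcomes. Healing, surgery and yeast infection can differ between two limbs of one child but are likely to be correlated, and the Cox, log-rank and logistic analyses make no allowance for that.

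**Working it through.** **The plan's own figure.** The plan gives no figure for pain, medication use or visits. Its only one is power for healing time: over 90% for a 2-day difference with SD 0.3, alpha 0.05 and 50 per group. The standard error is 0.3 × √(2/50) = 0.06, so the difference is 2/0.06 = 33 standard errors and power is essentially 100%. The figure holds as a lower bound but says nothing about the child-level tests.

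**Inputs.** Extremity as unit (IV.B), patient as unit of randomization (IV.C), t-test and chi-squared test (IV.F), 100 burns in total (IV.F). The share *b* of children with two study limbs is not given; 10% to 50% is an assumed range. No child is taken to have more than two.

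**Identical values.** Take *N* children in an arm and let σ² be the variance between children. There are *N*(1+*b*) rows, and the squared weights sum to *N*(1−*b*) + 4*Nb* = *N*(1+3*b*).

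- True variance of the mean: σ²(1+3*b*) / [*N*(1+*b*)²]
- Variance the test assumes: σ² / [*N*(1+*b*)]
- Ratio (design effect, DE): (1+3*b*) / (1+*b*)
- Actual two-sided type I error: 2 × [1 − Φ(1.96/√DE)]

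For example, at *b* = 0.3, DE = 1.9/1.3 = 1.46, 1.96/√1.46 = 1.62, and the type I error is 10.5%.

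**Correlated values.** If each limb is scored separately with within-child correlation ρ, DE = 1 + [2*b*/(1+*b*)]ρ. At an assumed ρ = 0.5 and *b* = 0.3 this is 1 + 0.3/1.3 = 1.23, giving 7.7%.

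| *b* | Children behind 100 rows, 100/(1+*b*) | DE, identical | Effective rows, 100/DE | Type I error, identical | Type I error, ρ = 0.5 |
|---|---|---|---|---|---|
| 10% | 91 | 1.18 | 85 | 7.1% | 6.1% |
| 20% | 83 | 1.33 | 75 | 9.0% | 7.0% |
| 30% | 77 | 1.46 | 68 | 10.5% | 7.7% |
| 40% | 71 | 1.57 | 64 | 11.8% | 8.4% |
| 50% | 67 | 1.67 | 60 | 12.9% | 9.0% |

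**Simulation check** (20,000 runs, 50 rows per arm, same five values of *b*).

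- Identical values, t-test: 7.4%, 8.6%, 11.4%, 11.9% and 14.2%.
- Identical values, chi-squared test: 8.2%, 9.8%, 11.8%, 12.9% and 14.3%, against 5.5% with no bilateral cases.
- ρ = 0.5, t-test: 6.5% to 9.6%.
- One row per child, t-test: 4.7% to 5.2%.
- Limbs rather than patients randomized, identical values, t-test: 4.9% to 5.2%.

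The simulation used whole children per arm (45, 42, 38, 36 and 33), so the simulated shares differ slightly from *b*; at 30%, for example, 12/38 = 32%. The last line shows that the inflation depends on randomizing the patient, which is what IV.C does.

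**The case against.** The strongest reply is that IV.F never says pain is analysed per extremity, and IV.A speaks of patient pain, so a sensible analyst might use one row per child anyway. That is possible, but the sentence in IV.B is unqualified and nothing later overrides it. If one row per child is intended, the plan should say so, or the unit can be chosen after the data are seen.

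Four stronger readings are tempting, and the documents do not support them.

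- **All pain scores are exact duplicates.** This holds for home pain and home medication use. FLACC and parent-perceived pain are tied to the dressing change, and a child with two burned limbs has two dressings changed. Each could be scored, and the plan does not say. Scores would then be correlated rather than identical, and the inflation smaller.
- **The cost tests are too liberal.** No cost test is named. Soft casts and dressings can properly be counted per limb; only clinic visits belong to the child.
- **Mean visits would be inflated in the arm with more bilateral children.** Duplicating rows reweights a mean. It shifts the mean only if children with two burned limbs have different visit counts, which the documents do not say.
- **Surgery on one hand censors the other.** The censoring sentence says patients while the data point is the extremity. That is a mismatch of wording, and a natural reading is that the operated limb is censored. It needs aligning, but it does not show that unoperated limbs would be censored.

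It is also fair that the bilateral share is unknown and that the outcomes most affected are secondary.

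**Conclusion.** The point stands in this form: a stated rule, followed as written, makes the named tests on child-level outcomes anti-conservative as soon as children with two burned limbs are enrolled. The direction is certain given patient-level randomization. The size is not, because it depends on the bilateral share. Over the assumed 10% to 50%, a nominal 5% type I error becomes about 7% to 13% for identical values (home pain, home medication use, demographics), and about 6% to 9% for dressing-change pain if it is scored per limb with correlation 0.5. The simulations agree or run slightly higher at most settings. For cost, the conclusion is limited to counting visits once per child.

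The change should be made. It is cheap, and it bears on one of the three hypotheses, though mainly on secondary outcomes.

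**What to change.** In sections IV.B and IV.F:

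1. Limit the separate-data-point rule to limb-level outcomes: re-epithelialization, surgery to that limb, yeast infection of that limb, and casts and dressings used on it.
2. Analyse home pain, home medication use, clinic visits and demographics with one record per child. Because pain is recorded at every follow-up visit, prespecify the per-child summary across visits.
3. State whether dressing-change pain is scored per child or per limb. If per child, apply item 2. If per limb, use GEE, a mixed model or cluster-robust variance.
4. For the limb-level Cox and logistic models, use cluster-robust variance by child, and use a clustered version of the log-rank test.
5. State the planned number of children as well as burns.
6. Reword the censoring sentence so that its unit, patient or extremity, matches the unit of analysis.

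This takes a few sentences and no new patients. Recording which limb a dressing-change score belongs to is needed only if scoring is per limb. The cost is a smaller n for the child-level analyses, for example 77 records rather than 100 at a 30% bilateral share. Little is truly lost, since the 100 duplicated rows carry the information of only about 68 independent ones.
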